6.13.3 Additional Secondary Efficacy Endpoints

6.13.3.1 Top 3 Caregiver Concerns Visual Analogue Scale (VAS)

Caregivers will be asked to rate three causes for concern by drawing a vertical mark on a 10 cm long VAS with anchors of "not at all severe" at the left end and "very severe" at the right end. The 3 concerns related to the subject's myotonic dystrophy will be chosen and rated at Visit and should not change for the duration of the study. The Top 3 Caregiver Concerns VAS is assessed at Visits and (Follow-up) and may be completed at home if required due to a COVID-19 related reason.

The Top 3 Caregiver Concerns VAS total score will be derived as the total of the VAS scores for the three concerns at each Visit regardless of any changes to the concerns rated. If fewer than three scores are available, the total score will be set to missing.

A sensitivity analysis will be conducted where the only the same concerns as recorded at Visit may be used in the derivation of the total score. If not all of the three concerns are rated at a particular visit, the total score will be set to missing.

A MMRM model will be fitted to the change from baseline to Visit and in the the Top 3 Caregiver Concerns VAS total score. The model will be fitted and results presented as described for the primary estimand in section 6.13.1.1.

The observed Top 3 Caregiver Concerns VAS total score and corresponding change from baseline will be summarised over time. In addition, the VAS total score at Visits and and the change from Visit will be summarised.

The observed Top 3 Caregiver Concerns VAS total score will also be presented over time using by subject line plots by treatment group. In addition, line plots will present the adjusted LS mean changes from baseline and SEs over time, as estimated by the MMRM model, by treatment group.

The Top 3 Caregiver Concerns data will be listed. The listing will include change from baseline for the individual concerns VAS scores as well as the total VAS scores.

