10.1.2.2 Top 3 Caregiver Concerns Visual Analogue Scale (VAS)

The Top 3 concerns VAS allows caregivers to identify their main three causes of concern, related to the subject's myotonic dystrophy, rather than these being pre-specified within a scale and then rating how these concerns have changed at specific time-points during the study.

Caregivers will be asked to rate three causes for concern by drawing a vertical mark on a 10 cm long VAS with anchors of "not at all severe" at the left end and "very severe" at the right end. Ideally, the caregiver should choose one item that relates to muscle function (such as problems with walking, drinking from a straw, or grip), one item that relates to cognitive abilities (such as problems with thinking, planning or concentration), and one item that relates to performing activities of daily living (for example, problems or difficulties brushing teeth, getting dressed or helping with household chores). The 3 concerns related to the subject's myotonic dystrophy will be chosen and rated at baseline. These 3 signs and symptoms will be rated again according to the schedule of events using the same scales and will be completed remotely in the subject's home if required due to a COVID-19 related reason.

A copy of the Top 3 concerns VAS is included in APPENDIX E: Caregiver Top 3 Concerns Visual Analog Scale (VAS).

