2.3 Study Endpoints

The study endpoints (relating to the estimand variables in section 2.2 above) are as follows. Note that the terms 'endpoint' and 'variable' may be used interchangeably throughout this SAP to refer to the measurement of interest:

The primary efficacy endpoint is:

 Change from baseline in Clinician-Completed Congenital DM1 Rating Scale (CDM1-RS) to end of treatment

The key secondary efficacy endpoint is:

 Clinical Global Impression - Improvement Scale (CGI-I) (also referred to as the CGI-C) at end of treatment

The secondary endpoints are:

- Change from baseline in Top 3 Caregiver Concerns VAS score to end of treatment
- Change from baseline in Caregiver Completed Congenital DM1 Rating Scale (CC-CDM1-RS) to end of treatment
- Change from baseline in Clinical Global Impression Severity Scale (CGI-S) to end of treatment
- Change from baseline in Clinician-Completed Congenital DM1 Rating Scale (CDM1-RS) - Independent Central Rater Score to end of treatment
- Clinical Global Impression Improvement Scale (CGI-I) Independent Central Rater Score at end of treatment
- Change from baseline in Clinical Global Impression Severity Scale (CGI-S) Independent Central Rater Score to end of treatment
- Change from baseline in 10-meter walk-run test (preferred speed and fastest speed) to end of treatment

The exploratory endpoints are:

 Change from baseline in DXA Scan measurement of total body lean/muscle mass to end of treatment

- Change from baseline in measurement of lip strength (via lip force meter) to end of treatment
- Change from baseline in Congenital and Childhood Myotonic Dystrophy Health Index (CC-MDHI) Parent Proxy Instrument to end of treatment
- Change from baseline in Autism Behavior Inventory Clinician (ABI-C) to end of treatment
- Change from baseline in standard scores of the Vineland Adaptive
 Behavior Scale to end of treatment
- Change from baseline in quantitative myometric measure of hand grip strength to end of treatment
- Change from baseline in NIH Toolbox Cognition Battery: Dimensional Change Card Sort Test to end of treatment
- Change from baseline in NIH Toolbox Cognition Battery: Picture Sequence Memory Test to end of treatment
- Change from baseline in Peabody Picture Vocabulary Test (PPVT) to end of treatment
- evelssample
- Serial blood pharmacokinetics of tideglusib

[figure not shown]
The Safety endpoints are:

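### The main Top 3 Caregiver Concerns VAS total ignores swapped concerns, so its change from baseline can compare different symptoms

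*SAP*

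**What the plan says.** The instrument is individualised. Under Protocol 10.1.2.2 the caregiver names and rates three concerns at baseline, and afterwards "These 3 signs and symptoms will be rated again according to the schedule of events using the same scales". SAP 6.13.3.1 agrees that the chosen concerns "should not change for the duration of the study". Each is marked on a "10 cm long VAS with anchors of" no severity and high severity.

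The same SAP section then defines the analysed total as "derived as the total of the VAS scores for the three concerns at each Visit regardless of any changes to the concerns rated". The only condition on that total is a count: "If fewer than three scores are available, the total score will be set to missing". The endpoint in SAP 2.3 is "Change from baseline in Top 3 Caregiver Concerns VAS score to end of treatment", and the analysis matches it: "A MMRM model will be fitted to the change from baseline".

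A second version is planned: "A sensitivity analysis will be conducted where the only the same concerns as recorded at Visit may be used". In that version the total is missing at any visit where not all three of those concerns are rated. The section also provides a listing of change from baseline for each individual concern. SAP 6.18, which records departures from the protocol's planned analysis, does not mention the unrestricted total.

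**The concern.** A change score means something only if the same thing is measured twice. A replacement concern has no baseline rating. Subtracting the baseline of the concern it displaced gives a number that is a change in neither. Because the total needs only three scores, a swap passes into the lead analysis unmarked.

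What is at stake is the reading of one secondary endpoint and whatever reuses its total. Section 2.5 of the SAP addendum uses the total in the run-in response subgroup analysis. Protocol 11.5 allows a supporting permutation test, with numerical superiority on secondary endpoints given as an example criterion. Under a criterion of that kind, a small shift could matter if the true difference is near zero.

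**Working it through.** The documents state no SD, effect size, power or swap frequency for this endpoint, so there is no figure to reproduce. The check has four parts.

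**1. The rules side by side.** Protocol 10.1.2.2 has the same three concerns re-rated, and the SAP says the concerns should stay fixed. The main total in the SAP accepts any three. If nobody swaps, the unrestricted and same-concerns totals are identical. They part only when the instruction is not followed, and the SAP foresees that, since it writes a rule for it.

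**2. Bound for one child.** Each concern is scored 0 to 10 cm, so the total runs from 0 to 3 × 10 = 30 cm. The error from one swap is the replacement's score minus the score the dropped concern would have had at that visit. This lies between −10 and +10 cm. An example with assumed scores: a concern falls from 8 to 3 cm and is replaced by one rated 7 cm.

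- Recorded change: 7 − 8 = −1 cm
- True change: 3 − 8 = −5 cm
- Error: −1 − (−5) = +4 cm

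**3. Effect on an arm mean.** Let f be the share of an arm with one swapped concern at end of treatment and g the average error. The arm mean shifts by f × g. If g is a constant, independent of the rest of the score, the added variance is f(1 − f)g². Both f and g below are assumptions.

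| f | g = 2 cm: shift (added variance) | g = 4 cm | g = 6 cm |
|---|---|---|---|
| 5% | 0.1 cm (0.19 cm²) | 0.2 (0.76) | 0.3 (1.71) |
| 10% | 0.2 (0.36) | 0.4 (1.44) | 0.6 (3.24) |
| 20% | 0.4 (0.64) | 0.8 (2.56) | 1.2 (5.76) |
| 30% | 0.6 (0.84) | 1.2 (3.36) | 1.8 (7.56) |

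These are shifts in one arm. With the same g in both arms, the bias in the treatment difference is (f_tideglusib − f_placebo) × g. At 20% against 10% with g = 4 cm it is 0.10 × 4 = 0.4 cm. At equal rates it is zero and only the added variance remains. A table entry equals the bias only if the other arm has no swaps. SAP section 3 reports 53 children randomized, about 26 per arm, so one 4 cm swap moves an arm mean by about 4/26 = 0.15 cm.

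**4. Would pro-rating from two retained concerns be better?** Take the same example and let each retained concern change by d cm (negative is improvement).

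- True change in the total: 2d − 5
- Unrestricted rule: 2d − 1, an error of 4
- Pro-rated (mean of the two × 3): 3d, an error of d + 5

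With d = 0, pro-rating errs by 5 cm against 4 cm. It does better only when −9 < d < −1, that is, when each retained concern improved by between 1 and 9 cm.

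**The case against.** The strongest reply is that the plan already deals with this. The same section pre-specifies the analysis restricted to the baseline concerns and lists individual concerns, so any effect of swapping will be visible. Both documents tell caregivers to keep the concerns fixed, so swaps may be few or absent. The content of the follow-up form in Protocol Appendix E is not shown, so it may carry the baseline concerns forward. The endpoint is supportive under SAP 6.14, without multiplicity control. All of this stands and limits the weight of the point. It does not make the lead result correct: a sensitivity analysis shows a difference but leaves the mismatched score as the reported one.

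A reader might go further and infer that caregivers tend to replace concerns that have resolved, so that the rule hides benefit in the better arm. That is plausible, but neither document says why or how often concerns change. A swap to a milder concern would work the other way. The direction of bias cannot be established.

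**Conclusion.** The point holds as a defect in how the main total is derived and in which of two planned analyses leads. After a swap, part of the score is not a change in any symptom. The bound of 10 cm per swapped concern on a 30 cm total follows from the scale alone. Every arm-level figure rests on assumed swap rates and errors. Bias in the treatment difference requires swapping, or its average error, to differ between arms; otherwise the main cost is precision.

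It might be inferred that the endpoint as a whole is invalid or that the trial's main conclusions are at risk. The documents support neither: the two totals coincide where nobody swaps, the same-concerns analysis is already planned, and the primary and key secondary tests do not use this score. The change is worth making because it is cheap and brings the analysis into line with the protocol.

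**What to change.** In SAP 6.13.3.1, exchange the two analyses. Make the MMRM on the total of the three concerns recorded at baseline the main analysis of this endpoint, and keep the unrestricted total as the sensitivity analysis. Report the number of children with a swapped concern by arm and visit. State which total the addendum's run-in subgroup analysis uses.

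The cost is mainly wording and one count table. Both totals are already specified, and the same-concerns version already requires concerns to be matched to baseline. The downside is that visits with a swap become missing and rely on MAR, which may fail if concerns are dropped because they resolved. Showing both analyses exposes this.

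Do not make a total pro-rated from two retained concerns the main rule. It assumes that the dropped concern changed like the others, although Protocol 10.1.2.2 ideally wants the three drawn from different areas (muscle function, cognition, daily living). At most, use it as an additional sensitivity analysis.

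If the change is made after unblinding, label it post hoc and present both results.

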6.13.3.2 Caregiver-Completed Congenital DM1 Rating Scale (CC-CDM1-RS)

The CC-CDM1-RS is completed by the caregiver to score the symptom severity of the domains that are clinically relevant in Congenital DM1. This scale is analogous to the Clinician Completed CDM1-RS. The severity of the caregiver's concern in each domain is scored by using a 5-point Likert Scale. Scores range from 0 = Not present to 4 = Very severe. The CC-CDM1-RS is assessed at Visits and may be completed at home if required due to a COVID-19 related reason.

The CC-CDM1-RS total score will be derived at each visit as the total score based on 11 domain ratings, with a higher score indicating worse symptom severity. If one or more of the 11 items is missing then the total score will be set to missing.

An MMRM model will be fitted to the change from baseline to end of treatment in the CC-CDM1-RS in a similar manner to the primary estimand (see Section 6.13.1). The MMRM model will contain treatment, age group, visit and treatment by visit interaction as fixed effects, baseline CC-CDM1-RS as a covariate.

The CC-CDM1-RS total score and corresponding change from baseline will be summarised over time. In addition, the CC-CDM1-RS total score at Visits and the change from Visit to will be summarised.

The change from baseline in CC-CDM1-RS total score will be presented over time using by subject line plots by treatment group. In addition, line plots will present the adjusted LS mean changes from baseline and SEs over time, as estimated by the MMRM model, by treatment group.

6.13.3.3 Clinical Global Impression – Severity Scale (CGI-S)

The CGI-S is a 7-point Likert type scale that requires the clinician to rate the severity of the subject's illness at the time of assessment, relative to the clinician's past experience with subjects who have the same diagnosis. Considering total clinical

experience, a subject is assessed on CGI-S at the time of rating from 1 = normal, not at all ill to 7= extremely ill.

The CGI-S is administered at Visit and and an an analysis and analysis analysis and analysis analysis and analysis and analysis and analysis and analysis analysis and analysis and analysis and analysis analysis analysis and analysis analysis analysis and analysis analysis analysis analysis and analysis analysis

An MMRM model will be fitted to the change from baseline to end of treatment in the CGI-S in a similar manner to the primary estimand (see Section 6.13.1). The MMRM model will contain treatment, age group, visit and treatment by visit interaction as fixed effects, baseline CGI-S and age group as covariates.

Summary statistics of observed values will be presented as both continuous and categorical with the associated change from baseline and categorical by visit and treatment for the in-clinic and telehealth visits separately. For subjects who have both an in-clinic and telehealth assessment, change from baseline in CGI-S will be calculated for both methods and summarised separately.

The CGI-S will be presented over time using by subject line plots by treatment group. In addition, line plots will present the adjusted LS mean changes from baseline and SEs over time, as estimated by the MMRM model, by treatment group.

For the 3 occasions in the study (Visit where dual telehealth and in-clinic assessments are conducted, summary statistics of the difference between the methods (in-clinic – telehealth) will be calculated and summarized using descriptive statistics over time. The intra-rater correlation will also be presented for each visit. A scatterplot for each visit will compare the observed value for the two methods for each subject, with in-clinic assessments being presented on the y-axis and telehealth on the x-axis. A linear regression line separately for each treatment will be included. A line plot will present the mean at each visit, with in-clinic and telehealth assessments being presented on the same plot. Bar charts of the CGI-S frequency over time will be produced for the in-clinic and telehealth interviews separately. The CGI-S score (1 to 7) for Visits and will be presented on the y-axis.

Data for in-clinic and telehealth assessments will be listed separately.

6.13.3.4 Independent Central Rater of CDM1-RS and CGI

The in-clinic and telehealth CDM1-RS and CGI interviews at Visits and are video recorded. In addition to the investigator ratings of the CDM1-RS and CGI, an independent central rater will also rate the CDM1-RS, CGI (CGI-I and CGI-S) for both the in-clinic and telehealth interviews using the video recordings.

These measures will be summarised and analysed in a similar way to the corresponding clinician completed versions.

For each visit summary statistics of the difference between the methods (independent rater in-clinic – clinician rated in-clinic) will be calculated and summarized using descriptive statistics over time. The intra-rater correlation will also be presented for each visit. A scatterplot for each visit will compare the observed value for each method for each subject, with independent rater in-clinic assessments being presented on the y-axis and clinician rated in-clinic on the x-axis. A linear regression line will be included.

This will be repeated with the in-clinic measurements replaced by the telehealth measurements.

The Independent Central Rater data for the CDM1-RS and CGI will be listed.

6.13.3.5 10 Metre Walk/Run Test

A 10-metre ambulatory test will be performed at the subject's preferred walking speed and then at the fastest speed possible. For each speed, the test should be repeated until 3 valid measures are obtained. The mean of repeated measurements for each speed will be derived for analysis. In the event that a subject does not complete a walk/run test, then the derivation will be based on the observed mean of the non-missing repeat assessments. The 10-metre walk/run test is assessed at Visits and

A MMRM will be fitted in a similar manner to the primary estimand (see Section 6.13.1) to the change from baseline over time in the time taken (seconds) to complete the 10-metre walk/run test for the mean preferred speed and fastest speed. Each model will include the baseline value and age group as covariates, treatment group and visit as fixed effects, and the treatment-by-visit interaction.

For preferred speed and the fastest speed separately, the mean (of the repeat assessments at a visit) in the time taken (seconds) to complete the 10-metre walk/run test will be presented using by subject line plots over time by treatment group. In addition, line plots will present the adjusted LS mean changes from baseline and SEs over time, as estimated by the MMRM model, by treatment group for the time taken (seconds) to complete the 10-metre walk/run test.

The 10-metre walk/run test data will be listed.

6.13.4 Exploratory Endpoints

6.13.4.1 Dual-energy X-ray Absorptiometry (DXA) Whole Body Scan of Lean Muscle Mass

The DXA scan measures bone mineral density, lean muscle mass, fat content, and total body composition. The primary assessment of interest in this study, from an efficacy perspective, is lean muscle mass. Subjects will have their lean muscle mass determined by a whole body DXA scan and the following parameters recorded in grams; arms, legs and total. The DXA scan is performed at Visits and

An ANCOVA will be fitted to the change from baseline to end of treatment in the DXA scan total lean muscle mass (g). The ANCOVA will include the baseline value as a covariate and treatment group and age group as fixed effects. Adjusted LS Means for the treatment group means at the end of treatment estimated by the above model will be presented, together with the associated SE, 95% CIs and 2-sided p-values.

DXA scan total lean muscle mass (g) and change from baseline will be summarised over time using summary statistics.

DXA scan data will be listed.

6.13.4.2 Measurement of lip strength (via lip force meter)

Lip strength will be measured using a mouthguard adaptation for the digital force meter. Subjects will insert the mouthguard between their incisors and their lips and hold as force is applied for 10 seconds with increasing force until the mouthguard is dropped. Measurements will be repeated until 3 valid times are obtained. Lip strength is assessed at Visits and

The mean of repeated measurements will be derived for analysis. In the event that a subject does not complete a lip strength test, then the derivation will be based on the observed mean of the non-missing repeat assessments.

A MMRM will be fitted to the change from baseline over time in the mean lip strength (Newtons) in a similar manner to the primary estimand (see Section 6.13.1). The model will include the baseline value as a covariate, treatment group, age group and visit as fixed effects, and the treatment-by-visit interaction.

The mean (of the repeat assessments at a visit) in lip strength will be presented using by subject line plots over time by treatment group. In addition, line plots will present the adjusted LS mean changes from baseline and SEs over time, as estimated by the MMRM model, by treatment group.

The lip strength data will be listed.

6.13.4.3 Congenital and Childhood Myotonic Dystrophy Health Index (CC-MDH1) Parent Proxy Instrument

The CC-MDHI Parent Proxy is a 19 category, 128-item Likert scale that covers multiple aspects of the specific phenotype of Congenital DM1, intended for completion by the caregiver of the subject. Each item offers 6 levels of severity ranging from "he/she doesn't experience this" to "it affects his/her life severely". The CC-MDHI will be administered at Visits and and Each item will be scored 0 (corresponding to "he/she doesn't experience this" to 5 (corresponding to "it affects his/her life severely").

The CC-MDHI total score will be derived at each visit as the total score based on the 128 items, and the score within each of the 19 categories will also be calculated. A higher score indicates worse symptoms or severity. If one or more items is missing, the scores will be imputed based on the values of the other items in that category in which the item is missing by taking the average of the non-missing items and multiplying by total number of items (non-missing and missing) included in the score. This will be done provided at least half of the items within a particular category are non-missing.

An ANCOVA will be fitted to the change from baseline to end of treatment in the CC-MDHI total score. The same will be done for the total scores in each of the 19 categories. The model will be fitted and results presented as described in section 6.13.4.1 for the DXA scan.

Summary statistics of observed values with corresponding change from baseline will be presented as continuous by visit and treatment. Line plots will present the adjusted LS mean changes from baseline to end of treatment and SEs, as estimated by the ANCOVA, by treatment group.

The CC-MDHI data will be listed.

